In phase I of the study 15 patients with posterior fossa lesions who require prolonged neurointensive care and in which any intracranial invasive intervention is indicated regardless of used technique or treatment modality will be enrolled in the study. The indication for posterior fossa lesion treatment will be decided on a case-by-case basis by our neurosurgical team irrespective of the study.

The study will start as a monocentric clinical trial (pilot study), and subsequently in phase II the study is planned to be continued as a multicentric trial.

In the majority of patients, ICP- and LICOX sensors are usually placed in the right frontal lobe and/or at the site of the lesion. In case of posterior fossa surgery, additional probes (ICP / LICOX) will be placed into the surgical field.

The neuromonitoring data will be recorded and analyzed. Additionally, demographic data, all treatment-related complications, and management of intracranial hypertension will be recorded.

All adverse effects will be noted and reported, even if no clinical consequence will ensue. Non-neurological complications such as cardiopulmonary complications will be documented separately.

After the invasive treatment of the posterior fossa lesion, all patients will undergo CT and/or MRI as standard of care within 72 hours after the intervention (the acute phase) as a protocol for detection of procedure-related complications. As standard of care, an additional follow-up MRI will be performed if needed. In stable patients a preoperative MRI will also be performed before invasive treatment

The following outcomes will be evaluated and analyzed: mean ICP, ICP pulse amplitude, respiratory waves, slow waves and the RAP (compensatory reserve) index of supra- and infratentorial ICP signals, transtentorial difference, brain tissue oxygenation, blood saturation, ASTRUP, and further vital parameters, peri- and postoperative morbidity and mortality, procedure-related morbidity including infection, hematomas, epilepsy, cerebral puncture, cranial nerve palsies, and CSF leaks, perioperative cerebral ischemia, long-term neurological morbidity and mortality, and overall neurological outcome.

Institutional review board will be obtained by the Ethics Committee of the Medical University Innsbruck, Austria. Informed consent will be acquired from all patients for participation in the study during the study period according to local requirements.

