All treatment techniques and MRIs will be performed as a part of routine clinical care and no modifications will be introduced in the treatment or the follow-up modalities currently used by the Department of Neurosurgery and Neuroradiology, with the exception of ^{31}P - MRS (see above).

VARIABLES AND PARAMETERS

Clinical data

The following demographic characteristics of treated posterior fossa lesions and outcomes will be documented and analyzed: type, location, size, shape, volume, technical success of treatment, recurrence, bleeding / rebleeding, perioperative morbidity and mortality, procedure-related morbidity including thromboembolic events, iatrogenic rupture, perioperative stroke, occurrence of complications related to lesion (e.g. mass effect, delayed ischemia, hydrocephalus, vasospasm, etc.) long-term neurological morbidity and mortality, and overall good neurological outcome

Cerebral multimodal neuromonitoring

ICP, brain oxygen partial pressure (PtO₂) / **LICOX®**, alternatively microdialysis, cerebral blood flow / **Hemedex®**, cortical spreading depolarization (CSD)

MRI (including DWI and ³¹P-MRS in selected cases)

Phosphocreatin (PCr), Phosphomonoester (PME), Phosphoethanolamin (PEth), Phosphocholin (PCho), Phosphodiester (PDE), Glycero-Phosphocholin (GPC), Glycero-Phosphoethanolamin (GPE), Anorganisches Phosphat (Pi), Adenosin-Triphosphat (α , β , γ ATP), Adenosin Diphosphat (ADP), Mg²⁺, pH

INTERVENTION/EXAMINATION

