All patients suffering from symptomatic posterior fossa lesions are first treated and stabilized in the emergency room and/or at the ICU. After the initial imaging (in most cases CT/CTA), if necessary, patients are transported to the OR and/or the angiosuite. After treatment, regardless of the used treatment modality and possibly after implementation of invasive multimodal neuromonitoring according to contemporary guidelines by patient impaired consciousness (e. g., with GCS≤8), implantation of multimodal neuromonitoring is performed – please find the details in the study protocol TIBI-study (AN2014-0201 339/4.6 – microdialysis, tissue perfusion measurement, ICP-measurement, LICOX) the patients are transported to the neurosurgical or neurological ICU. In each patient, MRI including ³¹P-MRS will be performed at different stages of treatment (the indication for neuroimaging will be decided on a case-by-case basis). As mentioned above, in stable patients a preoperative MRI will also be performed which may provide additional relevant information for patient treatment.

Simultaneously, data from invasive multimodal neuromonitoring and laboratory values will be acquired and evaluated during the ICU stay after treatment.

All methods are validated by an international collaborative ring trial, as they are used in routine.

Finally, outcome scores like the mRS and the Glasgow Outcome Scale will be recorded.

INSTRUMENTS

➤ ***Multimodal Neuromonitoring***

- ICP-measurement, Raumedic, Münchberg, Germany
- Brain tissue oxygen and brain temperature, Licox, Integra, Plainsboro, New Jersey, USA
- Cerebral microdialysis, CMA, Stockholm, Sweden
- Alternatively tissue perfusion measurement, Hemedex, Cambridge, MA, USA

DISSEMINATION

A part of this study will most likely be assigned as a clinical Ph.D.-project for the residents at the Department of Neurosurgery.

STUDY POPULATION (SPECIMEN / TEST PERSON / PATIENTS)

IN- AND EXCLUSION CRITERIA

INCLUSION CRITERIA

- Posterior fossa lesions with anticipated prolonged neurointensive critical care
- Patients older than 18 years
- Informed consent if applicable (unconscious patients will be also enrolled)
- No existing exclusion criteria

EXCLUSION CRITERIA

- Coagulation disorders
- Age < 18 years
- Pregnancy

INFORMED CONSENT OF TEST PERSONS / PATIENTS

All patients harboring posterior fossa lesion who meet the inclusion criteria will be enrolled in the study.

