Informed consent will be acquired from all patients for participation in the study during the study period.

All interventions and neuroimaging (e.g. MRI) will be performed as a part of routine clinical care and no modifications will be introduced in the treatment or the follow-up modalities currently used by the Department of Neurosurgery / Neuroradiology, except ^{31}P -MRS (see above).

CALCULATION OF THE NUMBER OF CASES

The study is designed as a prospective clinical trial (the sample of 30 patients was selected according to epidemiologic data and estimated annual incidence of posterior fossa lesions in Central Europe).

Regarding the complex patient cohort a high drop-out rate for MRI in the acute phase due to unstable patients with a consecutive infeasibility of MRI is to be expected.

ANALYSIS

Data collection

Clinical and procedural data will be collected prospectively. The adverse events are classified in three groups, according to their mechanism:

- * Lesion-related events
- * Intraoperative / intraprocedural (iatrogenic) events
- * Device-related problems

The outcome of adverse events is classified in four groups:

- * No clinical modification
- * Transient deficit(s)
- * Permanent deficit(s) (deficit(s) remaining at the 6-months follow-up)
- * Death

All-cause morbidity is defined as a modified Rankin score ≥ 3 . When the preoperative mRS was greater than 2, the all-cause morbidity is defined as any increase in the mRS value.

STATISTICAL ANALYSIS

The distribution of continuous variables will be described by using means and standard deviations, and discrete variables will be described as frequencies, percentages, and confidence intervals. The Clopper-Pearson exact method will be used to construct 95% confidence intervals (CIs).

The characteristics of both treatment groups will be compared by using Chi² test. All outcome results will be compared between the study groups by using a MannWhitneyU test, or Student t test where appropriate. P <0.05 is considered indicative of a statistically significant difference.

LITERATURE - REFERENCES

1. Mizunari T. [Clinical aspects and intracranial pressure monitoring in cases of traumatic posterior fossa hematoma]. *Nihon Ika Daigaku zasshi* 1990;57:334-343
2. Schroder R. [Expansive processes in the posterior cranial fossa and changes in intracranial pressure during the preoperative and postoperative period]. *Ceskoslovenska neurologie a neurochirurgie* 1982;45:306-314

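### Does the missing assessment time in the all-cause morbidity rule (mRS ≥ 3, or any increase) call for a change to the plan?

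*Combined protocol and SAP*

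**What the plan says.** The rule is under ANALYSIS, Data collection. All-cause morbidity is an mRS of 3 or more, with an exception for patients already impaired: "When the preoperative mRS was greater than 2, the all-cause morbidity is defined as any increase in the mRS value". No time is given.

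The outcome list under STUDY DESIGN, METHODS has an early item, "peri- and postoperative morbidity and mortality, procedure-related morbidity including infection", and a late one, "long-term neurological morbidity and mortality, and overall neurological outcome". VARIABLES AND PARAMETERS, Clinical data repeats the early item as "perioperative morbidity and mortality, procedure-related morbidity including thromboembolic events" and also lists long-term morbidity. Neither list uses the term all-cause morbidity.

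Two places bear on timing. INTERVENTION/EXAMINATION closes with "Finally, outcome scores like the mRS and the Glasgow Outcome Scale will be recorded". The adverse-event outcome classes, placed immediately before the mRS rule, include "Permanent deficit(s) (deficit(s) remaining at the 6-months follow-up".

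Two others bear on the patients' condition. The first inclusion criterion is "Posterior fossa lesions with anticipated prolonged neurointensive critical care". INTERVENTION/EXAMINATION opens with "All patients suffering from symptomatic posterior fossa lesions are first treated and stabilized in the emergency room and/or at the ICU".

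**The concern.** A binary endpoint built on a functional scale depends on when the scale is read. Early and late morbidity are separate outcomes here, and one undated rule could be applied to either. The sentence before the one on outcome scores concerns data collected in the ICU, so an ICU-stay score cannot be strictly excluded.

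Patients enter because a long stay in neurointensive care is expected. If survivors are severely disabled during that stay whatever happens to them, an ICU-stay score counts nearly everyone who was independent beforehand and nobody who was already at mRS 5. The rate would then mostly restate the case mix. The baseline score might also be open, since patients are stabilised before the intervention and an mRS from before the illness could be used instead. With 15 patients (METHODS) or 30 (CALCULATION OF THE NUMBER OF CASES), each reclassified patient moves the rate by 1/15 = 6.7 or 1/30 = 3.3 percentage points. The reading could be chosen after the data are seen.

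**Working it through.** The plan states no morbidity rate, so there is no figure to reproduce. The check codes the rule, compares the two times, and then asks which reading the text supports.

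**1. The rule.** A patient is a case if follow-up mRS ≥ 3 when preoperative mRS ≤ 2; otherwise if follow-up mRS > preoperative mRS. The 0–6 scale with death as 6 is an assumption, because the documents do not print the scale.

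| Preoperative mRS | Case at follow-up mRS |
|---|---|
| 0–2 | 3–6 |
| 3 | 4–6 |
| 4 | 5–6 |
| 5 | 6 only |

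On this scale death is a case at every baseline.

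**2. ICU stay against 6 months.** The ICU-stay grade of a survivor is assumed to be 4 or 5. The table gives the number of the six living 6-month grades (0–5) at which the two answers differ.

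| Preoperative mRS | ICU grade 5 | ICU grade 4 |
|---|---|---|
| 0–2 | 3 (grades 0–2) | 3 (grades 0–2) |
| 3 | 4 (grades 0–3) | 4 (grades 0–3) |
| 4 | 5 (grades 0–4) | 1 (grade 5) |
| 5 | 0 | 0 |

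These are counts of grades, not probabilities. At preoperative mRS 4 the ICU answer itself depends on whether the ICU grade is 4 or 5, so preoperative mRS alone does not decide it.

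**3. Size in an extreme case.** Take 15 survivors, all at preoperative mRS 0–2. The ICU reading gives 15/15 = 100% (Clopper-Pearson 95% CI 78.2–100%). If 3, 6 or 9 return to mRS 0–2 by 6 months (assumed), the rate is 12/15 = 80%, 9/15 = 60% or 6/15 = 40%; the last has CI 16.3–67.7%.

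Putting everyone at mRS 0–2 is only one possible case mix. Unconscious patients may be enrolled, and a survivor at preoperative mRS 5 is a non-case at both times. With an ICU grade of 5 and 30 survivors, shares of 0, 20, 50, 80 and 100% at preoperative mRS 5 give 30, 24, 15, 6 and 0 cases in the ICU. As that share rises, fewer patients can change status between the two times.

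**4. Is an ICU grade of 4–5 in the documents?** No. Eligibility requires only that a long stay is expected, and both METHODS and INTERVENTION/EXAMINATION provide for stable patients with a preoperative MRI. A score at the end of the ICU stay could reflect how the course went.

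**5. Baseline.** For a patient at mRS 0–2 before the illness and 3, 4 or 5 just before the intervention, the choice of baseline changes the answer at 1, 2 or 3 of the six living grades ({3}, {3,4}, {3,4,5}). But the text says preoperative, and a pre-illness score departs from that word.

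**6. Which time does the text support?**

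- The mRS is named with the Glasgow Outcome Scale as an outcome score and placed last in the sequence of care.
- The only dated follow-up is 6 months. It stands in the same subsection as the rule, just before it, and separates permanent from transient deficits.
- Early morbidity has its own measures. Procedure-related morbidity is listed by component event (infection, haematoma, cranial nerve palsy, CSF leak and others), and adverse events are classed by mechanism and outcome.

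Together these place the mRS rule with long-term morbidity at 6 months.

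**7. What rests on the rule?** The 30 patients come from epidemiology and incidence, not from a morbidity rate. No stopping or success criterion uses the rule. The safety hypothesis concerns added risk from the extra probes. All-cause mRS cannot attribute that risk; the device-related adverse-event class addresses it.

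**The case for a change.** The best case for a change is that the 6-month time belongs, as written, only to the permanent-deficit class. Perioperative morbidity cannot be a 6-month quantity, and safety is the first stated aim. STATISTICAL ANALYSIS also sends all outcome results to tests at P < 0.05. In the illustration, the intervals for 15/15 and 6/15 (78.2–100% and 16.3–67.7%) do not overlap, and a sentence or two would settle the matter.

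Part of this stands. The rule has no date beside it and is not assigned to a listed outcome, the enumeration is correct, and a written time would remove any freedom to choose later. A survivor at preoperative mRS 5 also cannot be counted at any time, although non-fatal harm in that patient would still appear in the adverse-event classes.

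The rest does not carry. The non-overlapping intervals come from an assumed ICU grade, assumed recoveries and one chosen case mix. That perioperative morbidity cannot be scored at 6 months is a reason to leave it to the adverse-event classes, not to apply the mRS rule in the ICU. The two readings are not equally natural. The question whether death counts largely answers itself on the 0–6 scale, and mortality is listed as an outcome in any case.

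**Conclusion.** No change follows. This is missing detail that an analyst would fill sensibly: score the rule at the 6-month follow-up against the last mRS before the intervention, count death as a case while reporting mortality as well, and describe early harm through the adverse-event classes. All of these elements are already in the plan or follow from the scale.

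The possible difference between readings is large only under assumptions outside the documents. In the illustration it is 100% against 40–80% of 15 patients, which requires every survivor to be at mRS 4–5 in the ICU, every patient at preoperative mRS 0–2, and 3 to 9 recoveries. Among survivors at preoperative mRS 5 it is nil. Under the natural reading the rule gives a sound descriptive rate, and neither the sample size nor any decision depends on it.

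The conclusion assumes the standard 0–6 scale and that the mRS is obtained at 6 months.

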
Importantly, the benefits of intracranial pressure (ICP) monitoring must be weighed against the associated risks and complications. The risks of ICP monitoring are related to the degree of invasiveness, the location of the device, the presence of systemic infections, the need to restrict patient movement, and monitoring drift or artificially low readings. Complications include infection, hematomas, epilepsy, cerebral puncture, cranial nerve palsies, and CSF leaks. In general, the incidence of complication has been quoted as from 1.1% to 7.7%.²⁸⁻³²

A major motivating factor in our routine use of postoperative ICP monitoring is that clinical parameters (for example, blood pressure, neurological status, pulse, and respiration) are not always reliable markers of increased ICP or impending neurological deterioration secondary to complications.^{10,33} Moreover, some authors have showed the safety of ICP monitoring in the posterior fossa.^{1,21,23-26}

AIMS OF THE STUDY

The goal of this study is to test whether direct infratentorial monitoring is a more efficacious method for detecting dynamic changes in the operative compartment and whether it is safe, in view of the critical structures within the region.

The motivation behind this study is to determine the value of ICP and brain tissue oxygenation monitoring (LICOX) in the infratentorial compared to the supratentorial space in patients with posterior fossa lesions. Our aim is also the immediate detection of any pertinent complications that are related to mass effect or swelling within the posterior fossa, leading to subsequent prompt intervention in these patients. With this in mind, postoperative multimodal neuromonitoring is a standard procedure at our intensive care unit. The additional intracranial infratentorial monitoring most likely is the most sensitive way to detect any relevant complications or lesions that may result in irreversible sequelae.

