- 4) facilitate the neurointensive care of these patients including ventilatory support, the use of positive end-expiratory pressures, continued osmotherapy, and patient positioning; ultimately
- 5) better understand of pathophysiological processes with
- 6) immediately identify of complications with subsequent prompt intervention if needed.

QUESTIONS

- * Is infratentorial multimodal neuromonitoring safe and feasible, and necessary?
- * Do data assessed by multimodal monitoring in the posterior fossa correlate with data from the supratentorial compartment?
- * Is infratentorial multimodal neuromonitoring able to timely predict complications such as local swelling, mass effect, vasospasm, ischemia, or infarction?
- * Is infratentorial multimodal neuromonitoring of value in daily clinical practice?

HYPOTHESES

- The intracranial multimodal monitoring in the posterior fossa is safe and feasible, without any increased risk due to additional probes.
- Data generated by infratentorial multimodal neuromonitoring do not completely correlate with data from standardized supratentorial multimodal neuromonitoring. There are significant differences in ICP- or brain tissue oxygenation values between the supratentorial and infratentorial compartments.
- The infratentorial multimodal monitoring immediately detects all relevant complications related to posterior fossa lesions including mass effect, local swelling, postoperative hematoma, ischemic events, decrease in the blood flow, vasospasm and inadvertent or prolonged vessel occlusion, or infarction, resulting in prompt therapeutic intervention if necessary.
- Additional information from infratentorial probes facilitate to maintain the critical patients including ventilatory support, the use of positive end-expiratory pressures, continued osmotherapy, and patient positioning.

CLINICAL RELEVANCE

Our prospective study can provide better guidance and optimization of clinical therapy through a comprehensive assessment of patients harboring posterior fossa lesions.

This study has very high potential to generate a new intellectual property, to yield discoveries improving the prediction of complications and monitoring the effects of treatments. The data will offer better understanding of pathophysiological mechanisms in posterior fossa lesions.

STUDY DESIGN

METHODS

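### The supra- versus infratentorial comparison is made within patients, but the only stated tests are for independent, undefined groups, and no unit of analysis is given

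*Combined protocol and SAP*

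**What the plan says.** The Statistical Analysis section contains the whole inferential plan. After descriptive statistics and Clopper-Pearson intervals it states "The characteristics of both treatment groups will be compared by using" a chi-square test, and then: "All outcome results will be compared between the study groups by using a MannWhitneyU test, or Student t test where appropriate". Significance is set at P below 0.05.

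Neither kind of group is defined anywhere. Methods and the inclusion section describe a single enrolled cohort with no control arm and no allocation. The only other groups mentioned are adverse-event categories.

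The study's own question is a within-patient one. The Aims section gives as its motivation to "determine the value of ICP and brain tissue oxygenation monitoring (LICOX) in the infratentorial compared to the supratentorial space". Under Hypotheses it says: "There are significant differences in ICP- or brain tissue oxygenation values between the supratentorial and infratentorial compartments". Under Questions it asks whether the data from the two compartments correlate. The section headed Present says both compartments will be monitored at the same time. The outcome list in Methods includes "index of supra- and infratentorial ICP signals, transtentorial difference, brain tissue oxygenation".

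On timing, Intervention/Examination says that "data from invasive multimodal neuromonitoring and laboratory values will be acquired and evaluated during the ICU stay after treatment". On probe placement, Methods says "ICP- and LICOX sensors are usually placed in the right frontal lobe and/or at the site of the lesion", followed by "In case of posterior fossa surgery, additional probes (ICP / LICOX) will be placed into the surgical field".

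**The concern.** Two probes in one patient give paired data. Mann-Whitney U assumes independent samples, and the t test is described as a comparison between groups and never as paired. The transtentorial difference is listed as an outcome, but no test is attached to it.

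The plan also does not say whether a patient contributes one value per compartment or every reading of an ICU stay. That choice decides the direction of the error. With one value each and positive correlation, the stated tests are too conservative and can miss a real difference. With serial readings pooled as independent, the same tests can reject far too often. A non-significant result and a significant one would both be hard to interpret. The study also aims to make infratentorial monitoring routine practice and to continue as a multicentre phase II, and this comparison would be part of the evidence for both.

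**Working it through.** **1. The two readings of the test sentence.**
- *The groups are the compartments.* The samples come from the same patients, so an independent-sample test is wrong.
- *The groups are something else.* The compartment hypothesis then has no stated test.
- On either reading there is no correlation method and no unit of analysis.

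**2. Inputs.** From the documents: n = 15 (Methods, phase I) or n = 30 (Calculation of the Number of Cases; chosen from incidence, so there is no power calculation to reproduce), and a 5% level, taken as two-sided. Assumed, because the documents give none: normal data, equal SDs, correlation r between compartments of 0.3/0.5/0.8, a shift of 0.5 or 0.8 SD, m readings per site, and an intraclass correlation (ICC). The Aims section itself says surgery can strongly disturb pressure equalisation, so a high r cannot be presumed.

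**3. One value per compartment per patient.** The unpaired test takes the variance of the mean difference as 2σ²/n; the true variance is 2σ²(1−r)/n. The ratio true/assumed is 1−r = 0.7/0.5/0.2. The large-sample size is 2·P(Z > 1.96/√(1−r)) = 1.9%/0.6%/<0.1%. Simulation (20,000 replicates; size at r = 0 from 8,000):

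| n | r | Mann-Whitney true size | Mann-Whitney power, 0.5 SD | Signed-rank power, 0.5 SD |
|---|---|---|---|---|
| 15 | 0 | 4.4% | 23% | 23% |
| 15 | 0.3 | 1.9% | 21% | 32% |
| 15 | 0.5 | 0.9% | 18% | 42% |
| 15 | 0.8 | <0.1% | 12% | 79% |
| 30 | 0 | 4.5% | 45% | 45% |
| 30 | 0.3 | 2.0% | 45% | 59% |
| 30 | 0.5 | 0.8% | 44% | 74% |
| 30 | 0.8 | <0.1% | 43% | 98% |

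At 0.8 SD and n = 30 little is lost: 88%/91%/98% against 94%/99%/100% at r = 0.3/0.5/0.8. The unpaired t test behaves like Mann-Whitney. If r were −0.3, its size would rise to 8% to 9%. The paired t test holds 4.9% to 5.1% throughout.

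**4. Serial readings pooled as independent, no true difference.** Each reading is a patient-by-compartment value (variance ICC, correlation r between compartments) plus reading noise (variance 1−ICC). If the noise is independent between probes, the variance ratio true/assumed is m·ICC·(1−r) + (1−ICC). For m = 24 and ICC 0.5:
- r = 0.3: 24 × 0.5 × 0.7 + 0.5 = 8.90
- r = 0.5: 24 × 0.5 × 0.5 + 0.5 = 6.50
- r = 0.8: 24 × 0.5 × 0.2 + 0.5 = 2.90

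The false-positive rate 2·P(Z > 1.96/√ratio) is then 51%/44%/25%. Mann-Whitney by simulation (n = 30, 4,000 replicates) gives 51%/44%/24%. Other settings, n = 30:

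| Readings per site | ICC | r = 0.3 | r = 0.5 | r = 0.8 |
|---|---|---|---|---|
| 24 | 0.2 | 33% | 27% | 14% |
| 24 | 0.8 | 60% | 55% | 35% |
| 6 | 0.5 | 22% | 17% | 7% |

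A paired t test on patient means stays at 4.5% to 4.8% in the case of 24 readings and ICC 0.5. A different split of the variance (patient 0.4, patient-by-compartment 0.05 to 0.2, the rest noise; 24 or 72 readings) gives 14% to 62% for the pooled unpaired t test.

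If simultaneous noise is also correlated at r, the ratio is (1−r)(1 + (m−1)ICC). For 24 readings and ICC 0.5 this is 8.75/6.25/2.50, or 51%/43%/22%, which is almost the same. Elsewhere it matters. With 6 readings, ICC 0.5 and r = 0.8 the ratio is 0.2 × 3.5 = 0.70, which gives about 2%. The number of readings at which the error turns from conservative to inflated is 1/(1−r) = 1.4/2/5 with independent noise, whatever the ICC. With shared noise it is 1 + r/((1−r)·ICC) = 1.9/3/9 at ICC 0.5.

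**5. Patients with one probe only.** Suppose 12 of 15 patients have both probes and the shift is 0.5 SD. Mann-Whitney on all values against signed-rank on the 12 pairs gives about 19%/17%/12% against 24%/32%/66% at r = 0.3/0.5/0.8, and 22% against 17% at r = 0.

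**The case against.** Student's t test can be run paired, and the plan leaves room for judgement about which test is appropriate. But the sentence compares groups, never mentions pairing, and names as its alternative a test that has no paired form. The unit of analysis and the correlation method would still be missing.

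Nothing in the plan says that readings will be pooled. Mean ICP and the RAP index are summaries over time, and the transtentorial difference is a within-patient quantity, so one summary per patient may well be intended. This stands: the false-positive figures are conditional, and under that intention the risk is a missed difference. They also depend on the noise model, and with few readings and high r the inflation can vanish. With 24 readings and r of 0.3 to 0.5 it remains under both noise models.

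Single-probe patients may be few. Department policy is supratentorial monitoring of all complex posterior fossa procedures, and posterior fossa surgery adds probes in the surgical field. Supratentorial-only data are plausible for patients treated without surgery; infratentorial-only data are less likely. The 12-of-15 split is an illustration.

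Finally, phase I is a 15-patient pilot, no hypothesis is named primary, and safety comes first among the aims. The Clopper-Pearson intervals suit the safety aim and are not in question. The compartment difference is still one of four hypotheses and is to be judged at P below 0.05.

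**Conclusion.** The concern holds, and the test sentence is wrong as written. On one reading the compartment hypothesis gets a test that ignores the pairing; on the other it gets none. This follows from the text alone.

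The size of the error rests on assumed values of r, shift, readings and ICC. With one value per compartment and a 0.5 SD shift, the power lost by Mann-Whitney against the signed-rank test runs from nothing at r = 0 to 55 points at r = 0.8 with n = 30 (98% − 43%) and 67 points with n = 15 (79% − 12%). If readings are pooled, the false-positive rate in the n = 30 settings of the independent-noise model above lies between 7% and 60%, and it can fall below 5% when noise is shared and readings are few. Since the plan fixes none of these choices, the direction of the error cannot be known in advance. This should be corrected before any analysis.

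**What to change.** Rewrite the Statistical Analysis paragraph as follows.

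1. Define the treatment groups and study groups, or delete those comparisons.
2. Make the patient the unit: one time-matched summary value per compartment, with the window and the summary stated.
3. For supra- versus infratentorial outcomes, replace the unpaired tests with a paired t test or Wilcoxon signed-rank test on the within-patient difference (for ICP, the transtentorial difference already listed in Methods), with a 95% CI. Name one variable, for example mean ICP, as the main comparison and call the rest exploratory: six compartment variables each tested at 5% would give 1 − 0.95⁶ = 26% family-wise error if independent.
4. If serial readings are analysed, use a mixed model with random effects for patient and patient-by-compartment.
5. For the correlation question, report the between-patient correlation of the summaries with its 95% CI, and a within-patient correlation only from serial data.
6. Count and describe patients with a probe in one compartment only, and leave them out of the paired test.

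Bias with limits of agreement is an optional addition.

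The cost is a rewritten paragraph and somewhat more analysis work, with no new data or patients. There is a slight power loss if r is near 0 and some patients have one probe (22% against 17% in the example above). The correlation will be imprecise: for an observed 0.5, Fisher's z gives a 95% CI of −0.02 to 0.81 at n = 15 and 0.17 to 0.73 at n = 30.
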